8.4 Safety Set

The **Safety Set** will include all subjects who received at least 1 dose of study drug. The Safety Set will be used to summarize subject demographics and baseline characteristics, and used for all safety analyses, unless otherwise specified.

9 STATISTICAL ANALYSIS

9.1 General Considerations

The Schedule of Assessments is provided in Section 3 of the CSP. The precision standards for reporting variables are provided in an internal Biometrics document that specifies the programming rules including the precision for derived variables.

Continuous variables will be summarized using the following descriptive summary statistics: the number of subjects (n), mean, SD, median, minimum value (min), and maximum value (max).

Categorical variables will be summarized using counts and percentages.

Baseline value, unless specified otherwise, will be defined as the most recent non-missing measurement (scheduled or unscheduled) collected before the first dose of study drug in the Treatment Period. For ECGs, baseline will be defined as the most recent pretreatment measurement (or the average of triplicate measurements, if the most recent pretreatment measurement is obtained in triplicate) before the first dose of study drug in the Treatment Period. For systolic and diastolic blood pressure, baseline will be defined as the most recent pretreatment measurement (or the average of triplicate measurements, if the most recent pretreatment measurement is obtained in triplicate) before the first dose of study drug in the Treatment Period. For UPCR (and UACR) data baseline value will be the average of UPCR (UACR) values from the 3 urine samples collected during screening for the purpose of assessing eligibility.

Change (absolute change) from baseline will be calculated as Post-baseline value – Baseline value.

Treatment-emergent (TE) Period will include the time from the first dose of study drug in the Treatment Period to either (1) the Safety Follow-up Visit, (2) ETT Visit if it replaces the Safety Follow-up Visit, or (3) the date of the last dose + 28 days for subjects who do not have a Safety Follow-up Visit. The TE Period will be used for safety analyses unless specified otherwise.

Unscheduled visits: Data obtained from unscheduled visits will be included in the analysis as follows:

- In scheduled visit windows per specified visit windowing rules
- In the derivation of baseline
- In the derivation of maximum and minimum values during TE period, and maximum and minimum change from baseline values during TE period for safety analyses
- In individual subject data listings as appropriate

Visit Window: The analysis visit windows for the protocol-defined visits are provided in [Appendix A](#).

Incomplete or missing data will not be imputed, unless specified otherwise.

Outliers: No formal statistical analyses will be performed to detect and/or remedy the presence of statistical outliers, unless specified otherwise.

Multiplicity: No multiplicity adjustment will be performed.

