8.1 Inclusion Criteria

The following criteria are applicable for Cohort 1 and Cohort 2:

- 1. Willing to sign and date an informed consent form (ICF).
- 2. Willing and able to comply with scheduled visits, treatment plan, study restrictions (Section 9.59.4), laboratory tests, contraceptive guidelines (Section 11.6.5), and other study procedures.
- 3. An *APOL1* genotype of *G1/G1*, *G2/G2*, or *G1/G2* obtained with a Vertex-approved clinical study assay.
- 4. Between the ages of 18 and 65 years, inclusive.
- 5. Body mass index (BMI) of 18.0 to 40.0 kg/m², inclusive, and a total body weight >50 kg.
- 6. FSGS diagnosed by kidney biopsy, with the exception of the tip variant, as confirmed through the eligibility review process.
- 7. There should be no plan to start, stop, or modify dosing for an angiotensin converting enzyme (ACE) inhibitor, angiotensin receptor blocker (ARB), neprilysin inhibitor, sodium-glucose co-transporter-2 (SGLT2) inhibitor, renin inhibitor, systemic corticosteroids, tacrolimus, mycophenolate, or cyclosporine from 28 days before Screening through the Follow-up Period.
- 8. Subjects who are on low-dose corticosteroids (prednisone ≤ 10 mg per day or prednisone equivalent) or on an allowed immunosuppressant (i.e. tacrolimus, mycophenolate, or cyclosporine) must be on a stable dose for 28 days before screening.
- 9. Estimated glomerular filtration rate (eGFR) ≥30 mL/min/1.73 m² (±10%) based on the Chronic Kidney Disease Epidemiology Collaboration (CKD-EPI) equation. ^{13, 14}

10. Subjects with eGFR \geq 30 (\pm 10%) to \leq 40 mL/min/1.73 m² must have tubulointerstitial fibrosis \leq 50% or described as no, mild, or moderate on their kidney biopsy.

The following criterion is applicable for Cohort 1:

11. A UPCR ratio of ≥ 3 g/g ($\pm 10\%$) and ≤ 10 g/g in the first morning void on 3 measurements collected on at least 3 separate days within a 7-day period, during the Screening Period. The average of the 3 measurements must meet this criterion.

The following criterion is applicable for Cohort 2:

12. A UPCR ratio of ≥0.8 g/g (±10%) and <2.7 g/g in the first morning void on 3 measurements collected on at least 3 separate days within a 7-day period, during the Screening Period. The average of the 3 measurements must meet this criterion.

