9.3 Rationale for Study Elements

9.3.1 Study Design

The study will be single-arm and open-label. All subjects will receive VX-147 for a total of 13 weeks. A placebo arm was not included because FSGS is a rare, severe disease with a very low likelihood of spontaneous remission. ¹⁵⁻¹⁷ This is the first study targeting the APOL1 pathway

in patients with FSGS, so the duration required for proteinuria levels to reach nadir is unknown. Clinical practice guidelines 18 for other therapies indicate that ≥ 4 months of therapy may be required for patients with nephrotic-range proteinuria to achieve complete remission (defined as UPCR <0.3 g/g). The duration of 13 weeks for this study was selected to allow the maximum treatment time supported by nonclinical data.

This is the first study in patients with FSGS, therefore subjects will receive 2 dose levels of VX-147 to characterize PK of VX-147 at 2 dose levels in this population. As shown in Figure 9-1, the 15 mg qd dose will be administered for 2 weeks and the 45 mg qd dose will be administered for 11 weeks. The 2-week duration for the 15 mg qd dose was selected based on an exposure-response model suggesting that a measurable decrease in proteinuria may be observed after 2 weeks of dosing. The 11-week additional duration for the 45 mg qd dose, provides a total of 13 weeks continuous dosing, which is the longest observation period supported by available nonclinical data.

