9.3.4.1 UPCR

Percent change from baseline in UPCR at Week 13 was chosen as the primary endpoint because proteinuria is a characteristic feature of FSGS and 1 of its main prognostic factors. Urine samples will be collected for UPCR using the first morning void, which is standardly used in clinical practice to determine accurate urine protein levels. As UPCR is variable within an individual, 3 samples will be taken during screening, Week 5, Week 9, and Week 13; and the average of the 3 values will be used to determine baseline, Week 5, Week 9, and end-of-treatment UPCR values, respectively.

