9.3.1.2 Analysis of the Primary Efficacy Variable

The primary efficacy endpoint will be analyzed based on combined Cohort 1 and Cohort 2. Subjects non-compliant with study drug will not be included in the analysis.

The primary analysis of the primary efficacy endpoint will be based on the following steps: (1) Log-transform the UPCR values to reduce skewness; (2) Calculate the mean of the change from baseline in log-transformed UPCR, corresponding standard error (SE) and 2-sided 80% CI; (3) The geometric mean and geometric standard error (GSE) will be calculated by back-transforming (exponential-transform) the corresponding estimates obtained in step (2). GMPC from baseline will be obtained as $[\text{geometric mean} - 1] * 100\%$. The corresponding 2-sided 80% CI will be calculated by $[\text{back-transforming (exponential-transform) the CI obtained in step (2)} - 1] * 100\%$.

The GMPC from baseline in UPCR at Week 13, GSE (%), along with the corresponding 2-sided 80% CI will be provided. In addition, the corresponding 2-sided 95% CI will be provided for descriptive purposes.

In addition, the primary efficacy endpoint will also be summarized in a similar way separately for Cohort 1 and Cohort 2.

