9.3.1.3 Supportive Analyses

There will be no supportive analysis for the primary efficacy endpoint.

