9.3.1.4 Sensitivity Analysis

No sensitivity analysis for the primary efficacy variable is planned.

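### The screening average that admits subjects is also the UPCR baseline, and this single-arm plan has no analysis showing how far selection moves the result; single-void visits also show a small false fall

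*SAP*

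**What the plan says.** **Baseline.** SAP 9.1 defines the UPCR and UACR baseline as the "average of UPCR (UACR) values from the 3 urine samples collected during screening for the purpose of assessing eligibility".

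**Entry.** Inclusion criteria 11 and 12 (protocol version 6.0, section 8.1) set a UPCR window for each cohort and say: "The average of the 3 measurements must meet this criterion". With the 10% tolerance on the lower limit, the windows are about 2.7 to 10 g/g (Cohort 1) and 0.72 to 2.7 g/g (Cohort 2).

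**No comparator.** Protocol 9.3.1: "A placebo arm was not included because FSGS is a rare, severe disease with a very low likelihood of spontaneous remission".

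**Variability.** Protocol 9.3.4.1 gives the reason for three voids: "As UPCR is variable within an individual". No figure is attached.

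**Analysis.** SAP 9.3.1.2: "The primary efficacy endpoint will be analyzed based on combined Cohort 1 and Cohort 2"; each cohort is also summarised separately. SAP 9.3.1.3: "There will be no supportive analysis for the primary efficacy endpoint". SAP 9.3.1.4: "No sensitivity analysis for the primary efficacy variable is planned".

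**Averaging.** SAP 9.3.1.1 and Appendix A note 5 define the Week 13 value as an average of up to three UPCR values; note 5a accepts a single one. Step (1) of 9.3.1.2 follows: "Log-transform the UPCR values to reduce skewness". Week 1, Day 15, Week 3 and the Part B visits have one void each.

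**Day 1.** A pre-dose void is scheduled, but note c to protocol Table 3-2 keeps it out of efficacy use.

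**The concern.** When one noisy measurement both admits a subject and serves as baseline, its error is selected along with the subject. Someone admitted just above a floor is more likely to have been measured high, and tends to fall back later without any drug effect. A cap does the reverse. A control arm would carry the same shift and cancel it; here nothing does. A low rate of spontaneous remission answers a different question from measurement variability.

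At stake is how the estimate is read, above all the separate Cohort 1 summary, where part of any fall may be selection. The visits with one void carry a second, unrelated shift. They include Day 15, the last visit on the first dose level.

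**Working it through.** **1. The plan's own precision figure.** One-sample t interval, n = 10, SD 0.672 (SAP 7.2): 1.383 × 0.672/√10 = 0.294, as stated. With n = 20: 1.328 × 0.672/√20 = 0.200. These give the scale.

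**2. Selection shift with no drug effect.** Let X be a subject's true log UPCR, normal with mean μ and SD τ, and let Y = X + error be the log screening average, with error variance

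e² = (void SD)²/3 + (week SD)².

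For a window from a to b:

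shift = (1 − ρ)(μ − E[Y | a ≤ Y < b]), with ρ = τ²/(τ² + e²).

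The windows come from section 8.1. Everything else is assumed, because the documents give no void SD, between-subject SD or screened distribution: void log SD 0.3–0.4, shared-week SD 0–0.3, τ 0.8–1.0.

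Cohort 1 at a screened median of 2 g/g (μ = 0.693):
- Least noise (void 0.3, week 0, τ 1.0): e² = 0.030; 1 − ρ = 0.030/1.030 = 0.0291; conditional mean 1.525; shift 0.0291 × (0.693 − 1.525) = −0.024, or −2.4%.
- Most noise (void 0.4, week 0.3, τ 0.8): e² = 0.1433; 1 − ρ = 0.1433/0.7833 = 0.183; conditional mean 1.492; shift 0.183 × (0.693 − 1.492) = −0.146, or −13.6%.

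Simulation with raw three-void averages, as the plan uses, gives nearly the same:

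| Screened median | Cohort 1 | Combined, equal cohorts |
|---|---|---|
| 2 g/g | −2.5% to −13.1% | −0.7% to −3.8% |
| 2.5 g/g | −1.8% to −10.0% | −0.1% to −0.7% |
| 3 g/g | −1.3% to −7.4% | +0.3% to +2.5% |
| 5 g/g | about 0 | against the drug |
| 6 g/g | +0.4% to +3.2% | against the drug |

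The formula puts the change of sign at about 5.2 g/g for Cohort 1 and 2.7 g/g combined. Cohort 2 moves against the drug at all these medians, which is why the combined figure is small near 2.7 g/g.

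**3. Averaging order.** The log of a raw three-void mean exceeds the mean of the three logs by roughly (void SD)²/3. Simulated values are 0.013, 0.030, 0.052 and 0.080 at void SD 0.2, 0.3, 0.4 and 0.5. One void against a three-void baseline therefore reads −1.3%, −2.9%, −5.1% and −7.7% with no true change. With three voids at both ends the excess cancels.

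**4. What a Day 1 baseline would give.** The third screening void is due by Day −5, so the Day 1 void plays no part in selection. With noise independent between weeks, mean log Week 13 voids minus log Day 1 void is within 0.4% of zero in each cohort.
- CI width relative to the primary: √(0.672² + (2/3)(void SD)²)/0.672 = 1.06 (void SD 0.3) to 1.11 (0.4).
- SE of primary minus check, Cohort 1: √((4/3)(void SD)² + 2(week SD)²)/√10 = 0.346/√10 = 0.11 up to 0.627/√10 = 0.20.
- Cohort 1 shift divided by that SE: about 0.1 to 0.7 at medians 2 to 3 g/g.
- If week-level fluctuation persists to Day 1 (correlation 0.3–0.5), some bias remains: up to about −2.5% to −4.4% in Cohort 1 at a median of 2 g/g.

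**The case against.** The strongest reply is that the primary analysis is the combined one. Its shift at medians 2 to 3 g/g is at most about 0.04 on the log scale, against a half-width of 0.200, and three-void averaging already limits the noise. That stands, and it keeps this short of a defect in the primary result. It does not cover the Cohort 1 summary.

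Five stronger readings are tempting, and the documents do not support them.
- **That selection must flatter the drug in Cohort 1.** The cap below 10 g/g pulls the other way, and the screened median is not given.
- **That the combined result is biased towards benefit.** The cohorts meet at 2.7 g/g and their shifts offset; the sign is unknown.
- **That false-positive rates are inflated.** This is an estimation study with no decision rule on whether the 80% CI excludes zero, so no planned error rate exists to inflate.
- **That the averaging order is missing.** The SAP reads as average, then log. The opening phrase on log transformation in protocol 12.3.3.1 could suggest otherwise, but that section also defines the Week 13 value as an average first. An explicit sentence would be editorial.
- **That the over-time analysis already supplies a contrast free of selection.** SAP 9.3.2.2 plans only changes from baseline at each visit, with no contrast between on-treatment visits. Part B is no clean check either: it is optional, and protocol 9.1.3 bars subjects whose UPCR stayed at or above 90% of baseline.

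It is also fair to say that a single Day 1 void cannot test for the bias: the expected gap is well under one SE in Cohort 1 at these medians. It can supply an alternative estimate.

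**Conclusion.** The concern holds in a limited form. Entry and baseline rest on one statistic, with no control arm and no sensitivity analysis, so selection error enters the change from baseline. Its size and sign cannot be derived from the documents. The figures above are conditional on the assumed SDs, a log-normal screened population and equal cohorts, although Cohort 1 is only up to 10 subjects. They are not bounds: one repeat of screening assessments and up to three rescreenings (protocol 9.1.1.1 and 9.1.1.3) are not modelled.

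The single-void artefact follows from the SAP's own rule. It affects exploratory visits, and reaches the primary endpoint only for a subject with fewer than three Week 13 voids. This should be fixed; it does not invalidate the primary analysis.

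**What to change.** 1. **Day 1 void.** Amend note c to protocol Table 3-2 so that UPCR and UACR may be derived from the existing Day 1 pre-dose void. Table 11-2 already lists urine protein, creatinine and albumin. Add a Day 1 pre-dose row to SAP Appendix A for this analysis only, since Day 1 falls in neither the baseline window (before Day 1) nor the Week 1 window (after Day 1).
2. **One sensitivity analysis.** Replace SAP 9.3.1.4 with mean log Week 13 voids minus log Day 1 void, combined and by cohort, in the same subjects and with the 80% CI. Report it as an alternative estimate little affected by selection, not as a test of the bias, and state its limits: a wider interval, an imprecise difference from the primary, and residual bias if fluctuation persists to Day 1.
3. **Single-void comparisons.** For UPCR and UACR at Week 1, Day 15 and Week 3, and for Part B UPCR, average log values, baseline included. Record the departure from protocol 12.3.3.2 in SAP 3.1. Report as a sensitivity result any Week 13 value based on fewer than three voids, handled the same way.

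The primary arithmetic calculation, eligibility and the Part B rule stay unchanged.

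**Cost.** One table-note amendment with the approvals in protocol 13.2.3, SAP wording, one Appendix A row and one table; no new sample. Log averaging puts some subjects' baselines below the arithmetic entry floor (about 2–10% of Cohort 1 and 0.5–4% of Cohort 2). If the whole over-time curve uses it, the Week 13 point may differ from the primary by about 1–1.6% (one SE at n = 20). Both need a footnote.

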9.2 Background Characteristics

9.2.1 Subject Disposition

Disposition summary will be provided by cohort and overall.

The number of subjects, based on the All Subject Set, in the following disposition categories, will be summarized:

- All Subjects Set
- Full Analysis Set
- Safety Set
- Follow-up Set

Treatment Period (Part A): The number and percentage of subjects, based on the FAS, in each of the following disposition categories, will be summarized:

- Completed treatment
- Prematurely discontinued treatment and the reason for discontinuation from treatment
- Completed Safety Follow-up Visit
- Completed study
- Prematurely discontinued the study and the reason for discontinuation from study

Off-treatment Follow-up Period (Part B): The number and percentage of subjects, based on the FAS, in the following disposition categories, will be summarized:

- Completed study
- Prematurely discontinued the study and the reason for discontinuation from study

A listing will be provided for subjects who discontinued treatment or who discontinued study with reasons for discontinuation.

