9.1.3 Part B

Participation in Part B is optional. After the last Part A Visit, subjects will be followed off-treatment at a visit scheduled every 4 weeks (\pm 2 weeks) to assess the change in proteinuria after stopping administration of VX-147 (Table 3-3). Part B visits will continue until the UPCR level reaches \geq 90% of baseline levels or 3 months after the last dose of study drug, whichever occurs first. If a subject has not achieved \geq 90% of baseline UPCR by the Part B Week 12 Visit, the Part B Week 12 Visit will be the last study visit.

Subjects will not be allowed to participate in Part B if (1) their UPCR level during Part A remained \geq 90% of baseline or (2) their UPCR level reached \geq 90% of baseline before the Part A Week 13 Visit and remained at that level through the Week 13 Visit.

The SFUV and Part B Week 4 Off-treatment Follow-up Visit may occur on the same day, provided the visit windows for both visits are met.

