12.2 Analysis Sets

The following analysis sets are defined: All Subjects Set, Full Analysis Set (FAS), Safety Set, and Follow-up Set.

The **All Subjects Set** will include all subjects who were enrolled in the study. This analysis set will be used for all individual subject data listings and disposition summary tables, unless otherwise specified.

The **FAS** will include all subjects who received at least 1 dose of study drug in the Treatment Period and have at least 1 post-baseline efficacy assessment. The FAS will be used to summarize subject demographics and baseline characteristics, and for all efficacy analyses in the Treatment Period, unless otherwise specified.

The **Follow-up Set** will include all subjects who entered the Off-treatment Follow-up Period (Part B) and have at least 1 efficacy assessment in that period. The Follow-up Set will be used for all efficacy analyses in the Follow-up Period, unless otherwise specified.

The **Safety Set** will include all subjects who received at least 1 dose of study drug. The Safety Set will be used for all safety analyses, unless otherwise specified.

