12.3.2 Background Characteristics

12.3.2.1 Subject Disposition

The number and percentage of subjects in each disposition category in the Treatment Period (e.g., included in the All Subjects Set, included in the Safety Set, completed Treatment Period, completed SFUV, and discontinued treatment or study with a breakdown of the reasons for discontinuation) will be summarized.

The number and percentage of subjects in each disposition category in the Off-treatment Follow-up Period (e.g., included in the Follow-up Set, completed Follow-up Period, and discontinued study/Follow-up Period with a breakdown of the reasons for discontinuation) will be summarized.

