8.2 Full Analysis Set

The **Full Analysis Set (FAS)** will include all subjects who received at least 1 dose of study drug in the Treatment Period and with at least 1 post-baseline efficacy assessment. The FAS will be used to summarize subject demographics and baseline characteristics, and for all efficacy analyses in the Treatment Period, unless otherwise specified.

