8.3 Follow-up Set

The **Follow-up Set** will include all subjects who entered the Off-treatment Follow-up Period (Part B) and have at least 1 efficacy assessment in that period. The Follow-up Set will be used for all efficacy analyses in the Off-treatment Follow-up Period, unless otherwise specified.

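### SAP 9.2.1 divides Part B completion and discontinuation by the FAS, which includes subjects who never entered Part B, so both percentages shrink by the share who entered

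*SAP*

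**What the plan says.** SAP 9.2.1 first gives counts of the All Subjects Set, FAS, Safety Set and Follow-up Set, by cohort and overall. It then sets the base for the two disposition tables.

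- Part A: "Treatment Period (Part A): The number and percentage of subjects, based on the FAS, in each of the following disposition categories". The categories are treatment completion or discontinuation, Safety Follow-up Visit (SFUV) completion, and study completion or discontinuation, with reasons for discontinuing.
- Part B: "Off-treatment Follow-up Period (Part B): The number and percentage of subjects, based on the FAS, in the following disposition categories". There are two categories, study completion and premature study discontinuation with reasons.

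It also plans a listing of everyone who discontinued treatment or study, with reasons.

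The relevant sets are:

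- FAS (SAP 8.2): "all subjects who received at least 1 dose of study drug in the Treatment Period and with at least 1 post-baseline efficacy assessment".
- Follow-up Set (SAP 8.3): "all subjects who entered the Off-treatment Follow-up Period (Part B) and have at least 1 efficacy assessment in that period".
- All Subjects Set (Protocol Version 6.0, 12.2, repeated in SAP 8.1): "This analysis set will be used for all individual subject data listings and disposition summary tables, unless otherwise specified".

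Protocol 12.3.2.1 illustrates Part B disposition with categories such as "included in the Follow-up Set, completed Follow-up Period". On entry, Protocol 9.1.3 says "Participation in Part B is optional" and excludes subjects whose UPCR stayed at 90% or more of baseline, or returned to that level before Week 13 and remained there. Protocol 9.1.2.3 excludes subjects who terminated treatment early.

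**The concern.** A disposition percentage should be taken over the subjects who could have had the outcome. In Part B those are the subjects who entered it. FAS membership is settled in Part A and does not depend on Part B entry, so the Part B table mixes two questions: how many entered, and how many of those stayed. It has no category for subjects who never entered, and the SAP does not say how to classify them.

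In Part A, the FAS requires an efficacy measurement after baseline. A dosed subject who leaves without one is missing from both the numerator and the denominator of the discontinuation rate.

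What is at stake is descriptive reporting. The study is a single-arm estimate in about 20 subjects, the primary analysis excludes subjects non-compliant with study drug (SAP 9.3.1.2), and no sensitivity analysis is planned (SAP 9.3.1.4). Readers will use the disposition tables to judge attrition behind that estimate and behind the Part B UPCR results.

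**Working it through.** The plan states no disposition percentage, so there is no figure to reproduce. Its one precision figure (0.294 on the log scale for 10 subjects) has no bearing here. The documents also give no dropout or Part B uptake rate, so the counts below are assumptions shown over a range. Planned enrolment is up to 10 plus approximately 10 (Protocol 12.1), taken as 20.

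**Part B.** Let F be the FAS size, m the number of FAS subjects entering Part B, d the entrants who discontinue, and c = m − d the entrants who complete. Assume subjects who never entered are placed in neither category.

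- Completion under SAP 9.2.1: c/F = (c/m) × (m/F)
- Discontinuation under SAP 9.2.1: d/F = (d/m) × (m/F)

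Both rates are scaled by m/F. They add to m/F rather than to 100%. With F = 20 and d = 1:

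| Entrants m | Completed, FAS base | Completed, entrant base | Discontinued, FAS base | Discontinued, entrant base |
|---|---|---|---|---|
| 5 | 4/20 = 20% | 4/5 = 80% | 1/20 = 5% | 1/5 = 20% |
| 10 | 9/20 = 45% | 9/10 = 90% | 1/20 = 5% | 1/10 = 10% |
| 15 | 14/20 = 70% | 14/15 = 93.3% | 1/20 = 5% | 1/15 = 6.7% |
| 20 | 19/20 = 95% | 19/20 = 95% | 1/20 = 5% | 1/20 = 5% |

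On the FAS base, one Part B dropout always reads 5%, whether 5 or 20 subjects entered. If subjects who never entered were instead counted as study completers, the m = 10 row would show (9 + 10)/20 = 95% completed, with discontinuation still 5%. The text does not say which applies.

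**Part A: who leaves the FAS.** Day 1 urine is not used for efficacy (Protocol Table 3-2, footnote c), so the first scheduled efficacy sample is Week 1, Day 8. Urine is also scheduled at the Early Termination of Treatment (ETT) Visit (Table 3-2) and at the SFUV (Table 3-3), where efficacy use is stated. The FAS definition has no on-treatment condition. On the scheduled visits, an early dropout is therefore excluded only if Week 1, ETT and SFUV samples are all missing. Consent withdrawal in the first week is the clearest route, because no assessments follow it (Protocol 9.1.2.3).

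**Part A: size.** Let N be the number dosed, x those with no post-baseline efficacy sample, and y the other discontinuations.

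- FAS base: y/(N − x)
- Safety Set base: (x + y)/N

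With y = 0:

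- One cohort, N = 10, x = 1: 0/9 = 0% against 1/10 = 10%.
- Both cohorts, N = 20, x = 1, 2, 3: 0/19, 0/18, 0/17, all 0%, against 5%, 10%, 15%.
- x = 0: no difference.

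**Consistency within the SAP.** Exposure, including a category for one week or less (9.2.5), and adverse events leading to treatment discontinuation (9.4 and 9.4.1) use the Safety Set. A subject who stopped for an adverse event and gave no later urine would be 1/10 in the adverse event table, while the disposition table showed 0/9 discontinued.

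**The case against.** The case for leaving the text alone has real substance.

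- **Protocol.** A reader might infer that the SAP breaches the protocol's assignment of disposition to the All Subjects Set. It does not: that default yields where another set is specified, and SAP 9.2.1 specifies one. Protocol 12.3.2.1 lists example categories and fixes no denominator.
- **Early dropouts.** A reader might infer that they disappear from the report, or that a tolerability signal is hidden. The documents do not support this. Safety Set minus FAS counts show how many dosed subjects are missing, and the listing, on the All Subjects Set by default, gives their reasons. They also appear in the exposure table and, where an adverse event was the cause, in the table of adverse events leading to discontinuation. Most early stoppers should stay in the FAS through an ETT or SFUV sample.
- **Re-basing.** Counts are printed beside percentages, and with about 20 subjects a reader can redo the division.
- **Uptake.** The Part B effect depends on an uptake the documents do not give.

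These points limit the size of the problem, and the Part A half becomes minor. They do not justify the Part B base. The only printed figure close to the number of entrants is the Follow-up Set count, which omits entrants without a Part B efficacy assessment, so re-basing from it is approximate. Optional entry and the entry bars make full uptake unlikely.

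**Conclusion.** The concern holds for Part B and, in a narrow form, for Part A.

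In Part B the stated rule multiplies both completion and discontinuation by entrants/FAS: halved at 50% uptake, quartered at 25%, unchanged at 100%. This assumes that subjects who never entered fall in neither category; the SAP should settle that point anyway.

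In Part A, each dosed subject with no post-baseline urine at all lowers the tabulated discontinuation rate by about 10 percentage points in a cohort of 10, or about 5 in 20. The effect is nil if there is no such subject, and other outputs still show the subject if there is one.

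A reader might go further and infer that the primary result is affected. It is not: this section governs descriptive tables only, and the Week 13 UPCR estimate does not use these percentages. The change is worth making because the rule yields misleading printed percentages and is easily corrected.

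**What to change.** In SAP 9.2.1:

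1. Base Part B disposition percentages on all subjects who entered Part B, and define entry. Do not substitute the Follow-up Set, because it would drop entrants who left before giving a Part B efficacy sample.
2. Add a line for subjects who did not enter Part B, split into declined and not eligible.
3. Base Part A disposition percentages on the Safety Set, in line with the exposure table and the table of adverse events leading to discontinuation. Enrolled but undosed subjects remain visible through the set counts.

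The cost is a few lines of SAP text, one Part B entry flag and a revised table shell. No new data are needed: Part B entry is already required to build the Follow-up Set, and the reasons for non-eligibility follow from early termination and UPCR records. The SAP introduction provides for documenting such a revision by amendment before database lock, or in the clinical study report after it.
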